5.2. Tenofovir disoproxil fumarate

5.2.1 General information

Tenofovir disoproxil fumarate (tenofovir DF) is a prodrug of tenofovir. It is an acyclic nucleotide phosphonate analogue of adenosine 5 monophosphate. The medication is stored at room temperature.

5.2.2 Pharmacokinetic considerations

Tenofovir DF is well absorbed from the gastrointestinal tract and after being taken up intracellularly is hydrolyzed rapidly to tenofovir and phosphorylated by cellular nucleotide kinases to the active form, tenofovir diphosphate. Tenofovir diphosphate competes with the natural intracellular deoxyadenosine triphosphate for uptake into the nascent viral DNA molecule and once incorporated causes DNA chain termination. Tenofovir diphosphate may also interfere with the HBV DNA polymerase by binding to the active catalytic site. The intracellular half-life of tenofovir is prolonged and is in excess of 60 hrs. The half-life of tenofovir in serum is about 17 hours following a single dose. Multiple dose pharmacokinetics suggests that the median steady state tenofovir C_{max} values are 355 mg/L [0.33 μ g/mL] after 48 weeks. Food does not affect absorption or pharmacokinetics. No demographic variables appear to affect tenofovir pharmacokinetics across either healthy participants or participants infected with HIV or HBV. Tenofovir is excreted unchanged in the urine and dose adjustments are needed in participants with renal insufficiency.

Dose adjustments are required for creatinine clearance (CrCl) of <50 mL/min.

	Creatinine Clearance (mL/min)			Hemodialysis
	>50	30-50	10-29	
Recommended 300 mg dosing interval	Every 24 hours	Every 48 hours	Every 72 to 96 hours	Every 7 days or after a total of approximately 12 hours of dialysis

Only when there is moderate CrCl (30-50 mL/min) or severe reduction in CrCl (<30mL/min) is there the chance for drug toxicity after a single 300 mg dose.

In vitro, tenofovir DF at expected concentrations with once a day dosing does not inhibit the metabolizing ability of major human cytochrome P-450 isoforms (CYP1A2, CYP2C9, CYP2C19, CYP2D6, and CYP3A4) responsible for phase I metabolism of most drugs.

Drug interactions potentially could occur with other drugs which are eliminated by proximal tubular secretion e.g. cidofovir, acyclovir and other members of this group of agents. Such a drug interaction may result in increased blood levels of tenofovir DF or the competing agent. Similarly there may be some interactions with drugs used in the treatment of HIV e.g. didanosine, atazanavir and lopinavir/ritonavir.

There is no substantial effect of TDF on methadone, estrogens or birth control pill pharmacokinetics.

5.2.3 Safety

Tenofovir DF is freely excreted unchanged by the kidneys by glomerular filtration and tubular secretion. High levels of tenofovir DF in renal tubules may interfere with renal function in a dose-dependent manner. Reports of hypophosphatemia, renal tubular toxicity and renal failure exist. This tubular toxicity manifests as renal tubular acidosis, a Fanconi-like syndrome or nephrogenic diabetes insipidus (22). Probably as a consequence of the nephrotoxic effects of tenofovir DF, osteomalacia has been reported in young macaques given 25 times the recommended dose. The osteomalacia observed may have been the result of chronic hypophosphatemia caused by tubular phosphate leakage. For this reason, use of tenofovir DF currently is not recommended in children.

To date most studies examining bone density in participants on prolonged therapy with tenofovir DF have been in participants with HIV infection. Osteopenia and osteoporosis have been reported but with no significant difference in the frequency of these complications in participants with HIV who are and who are not taking tenofovir.

Reproductive Toxicity: Tenofovir DF is a Pregnancy Category B drug. No adverse effects on embryo-fetal development in rats were observed with long-term, high-dose therapy; nor were there adverse effects on growth, development, and behavior. In this study, females of childbearing potential will be enrolled only if they agree to use effective contraception during therapy and pregnancy testing will occur at every visit during the peginterferon treatment phase.

5.3 Peginterferon-alfa-2a

5.3.1 General description

Peginterferon alfa-2a is a covalent conjugate of recombinant alfa-2a interferon with a single branched molecule of polyethylene glycol with a molecular weight of approximately 40,000 daltons. Peginterferon alfa-2a is produced using recombinant DNA technology and contains 180 µg/1.0 mL in vial form and the same amount per 0.5 mL in a prefilled syringe. The drug must be kept refrigerated at +4C until use.

Interferon inhibits viral replication by inducing an antiviral state in cells. Interferon does not enter the hepatocyte, but rather binds to specific receptors on the cell surface, which initiates intracellular signaling that leads to rapid activation of multiple "interferon-stimulated genes (ISGs); the encoded proteins of these genes inhibit viral replication in infected hepatocytes by multiple mechanisms (including inhibition of viral protein synthesis and breakdown of viral RNA). Peginterferon alfa-2a also has immunomodulatory activity that is thought to be important in obtaining a virological response. Steady-state serum concentrations of peginterferon alfa-2a are reached within 5 to 8 weeks using once weekly dosing. The mean terminal half-life after subcutaneous dosing is 160 hours compared to 5 hours for standard alpha interferon.

5.3.2 Pharmacokinetic considerations

In participants with end-stage-renal-disease undergoing hemodialysis, there is a 25% to 45% reduction in clearance of peginterferon alfa-2a. The effect of milder renal impairment has not been studied but it is advised that in participants with impaired renal function, signs and symptoms of interferon toxicity should be closely monitored. It is also recommended that peginterferon alfa-2a be used with caution in participants with creatinine clearance < 50 mL/min.

There is no known effect of peginterferon alfa-2a on the pharmacokinetics of drugs metabolized by the cytochrome P-450 system. There are no known clinically significant interactions with nucleos(t)ide analogue therapy, but a phase IV registration trial of peginterferon alfa-2a and telbivudine was prematurely discontinued due to a higher than anticipated incidence of peripheral neuropathy.

5.3.3. Safety

As with standard alpha interferon, treatment with peginterferon alfa-2a is associated with many troublesome and occasionally serious, or even life-threatening, side effects. Dose discontinuation has been reported in 6% to 9% and dose modification in 31% to 47% of participants treated in the peginterferon alfa-2a registration trials for hepatitis B. The most frequent causes of dose adjustment were laboratory abnormalities such as

thrombocytopenia or leukopenia. These side effects are particularly common in patients with advanced liver disease and hypersplenism. Peginterferon alfa-2a is contraindicated in participants with decompensated cirrhosis due to the possibility of serious infections, flares of disease, and worsening decompensation. In this study, patients with any clinical or laboratory features suggestive of hepatic decompensation will not be enrolled.

The majority of clinical experience in the use of peginterferon alfa-2a has been in chronic hepatitis C in which peginterferon is combined with ribavirin. In the few studies of peginterferon alfa-2a in chronic hepatitis B it has appeared that side effects are less frequent than in chronic hepatitis C. The overall incidence of serious adverse events was less in studies in hepatitis B (4%-5%) than in those with hepatitis C (7% to 16%), and fewer drug withdrawals were reported (6% to 8% versus 17% to 33%, respectively) despite similar doses and durations of therapy. Depression was also less frequently reported in studies done in hepatitis B (4%) than hepatitis C (22%, $p < 0.001$).

Peginterferon should be avoided in participants with other serious co-morbid illnesses, including, but not limited to, coronary artery disease, cerebrovascular disease, serious autoimmune conditions and severe depression.

Pregnancy:

Peginterferon alfa-2a is a Pregnancy Category C drug that has not been adequately evaluated in humans for its teratogenic effect. Standard interferon has been shown to increase the rate of abortion in Rhesus monkeys when given approximately 20 to 500 times the human weekly dose. Interferon, however, is highly species specific in its effects and animal studies may not reliably reflect the potential of side effects in humans. There have been no adequate and well-controlled studies of peginterferon alfa-2a in pregnant females. Therefore, in this study, females of childbearing potential will be enrolled only if they agree to use effective contraception during therapy and pregnancy testing will occur at every visit during the peginterferon treatment phase.

5.4. Administration and drug accountability

Study drugs (peginterferon alfa-2a, tenofovir DF, and emtricitabine/tenofovir) will be shipped to study sites from the drug distribution center. Staff at each site will be responsible for drug accountability. This will include documenting drugs received, study drug dispensed to participants, used and unused study drug returned, and accounting of any drug destroyed by the site. An accurate and up-to-date accountability log will be maintained by each site.

5.5. Concomitant medications

All concomitant medications (prescription and non-prescription) being taken by each participant will be queried and recorded by the study coordinator at each visit.

5.6. Prohibited medications

Use of the following medications is prohibited while participants are on study drugs:

1. Antivirals with activity against HBV, including famciclovir or valacyclovir. The need for ongoing use of these antivirals would be exclusionary at study entry, but allowed if medically indicated and prescribed during the course of the study.
2. Nephrotoxic agents including aminoglycoside antibiotics, amphotericin, cidofovir, and foscarnet.
3. Competitors of renal excretion such as probenecid and sulfipyrazone.
4. Systemic chemotherapeutic agents (i.e., cancer treatment medications).

5. Systemic corticosteroids. The need for ongoing use of systemic corticosteroids would be exclusionary at study entry, but would be recorded as a concomitant medication if medically indicated and prescribed during the course of the study.
6. Any investigational agents.
7. Use of growth factors such as GCSF, erythropoietin, and eltrombopag.

6. Study procedures

6.1. Study enrollment

Participants thought to be eligible for participation will be asked to give their consent to participate by discussions with study physicians and coordinators and by signing a current consent form approved by the IRB/REB at that institution. Participants will be required to sign the consent form before any study procedures are performed. They will then undergo the screening (8 weeks prior to randomization) procedures, including medical history, physical examination and blood tests as summarized in the Time and Event chart (Appendix 3). Once eligibility is confirmed, they will complete pre-randomization tests and then be randomly assigned (at baseline visit, day 0) to one of the two treatment groups using a system established by the Data Coordinating Center (DCC). Patients who are not currently enrolled in the HBRN Cohort study may be enrolled concurrently with the screening visit for this trial, or if they choose not to enroll into the Cohort Study, the necessary components on the Cohort baseline evaluation will be completed prior to enrolling in this study at the clinical trial screening or baseline visit.

6.2. Pre-randomization (screening) assessment

All participants are required to have a liver biopsy that is adequate for assessment within 144 weeks of randomization. The pre-treatment biopsies will be read by the local consortium pathologist, judged with respect to adequacy for assessing stage and grade, and whether it meets histologic criteria for entry. All slides will be re-reviewed centrally for subsequent data analysis.

The following assessments must be obtained within 8 weeks (56 days) prior to randomization.

1. Written informed consent.
2. Detailed medical history.
3. Physical examination, including pulse, blood pressure, temperature.
4. Limited clinical evaluation including anthropometric measures.
5. Depression assessment.
6. If baseline evaluation for Cohort Study is combined with trial screening visit, complete the Cohort Screening Log and Baseline Evaluation forms (coordinator, participant, and investigator).
7. Blood tests including CBC with differential, routine biochemical tests (including ALT, AST, total bilirubin, direct bilirubin, albumin, total protein, alkaline phosphatase, creatinine [including calculated CrCl], serum uric acid, BUN, calcium, phosphate, vitamin D, triglycerides, glucose, TSH, PT/INR, alpha-fetoprotein, anti-HCV and anti-HDV (if not available within the prior 144 weeks), anti-HIV, and HBV serologies
8. Urinalysis.
9. Pregnancy test for females of childbearing age.
10. Blood samples for qualitative HBsAg and HBeAg, anti-HBs, anti-HBe, HBV DNA, HBV precore/BCP, and antiviral resistance. Plasma and serum samples will be stored at each visit.

11. Blood samples for HBV genotype and/or subtype will be obtained if not available from samples drawn for the HBRN Cohort study.
12. Dual energy X-ray absorptiometry (DEXA) scan for bone density if clinically indicated (as standard of care).
13. A CT or MRI is required for patients with alpha fetoprotein greater than 20 ng/mL as clinically indicated to rule out HCC.
14. In participants with diabetes or hypertension, a retinal examination will be performed as standard of care unless done in the previous 48 weeks.

There are two ALT levels and HBV DNA levels required to qualify for randomization, with the most recent for ALT being within 8 weeks prior to randomization and the most recent for HBV DNA being within 32 weeks of randomization.

6.3. Baseline visit (day 0)

The baseline visit (day 0) will coincide with randomization and the start of therapy. The baseline visit will consist of:

1. Limited clinical evaluation.
2. Review of adverse events and concomitant medications.
3. Drug dispensing; instructions on their use, including education on self-injection with peginterferon alfa-2a (if appropriate).
4. Questionnaires (symptoms, quality of life, health behaviors, and fatigue).
5. Depression assessment.
6. Blood tests including CBC with differential, hepatic and renal panel, albumin, total protein, alkaline phosphatase, and PT/INR.
7. Urinalysis, urine creatinine, and urine phosphate.
8. Pregnancy test for females of childbearing potential.
9. A blood sample for storing serum and plasma for future research.
10. Blood samples for qualitative HBeAg, anti-HBe, quantitative HBsAg, quantitative HBeAg, and HBV DNA testing.
11. Blood sample (with consent) for DNA extraction and genetic testing will be drawn if not obtained as part of the Cohort Study. This may be collected at a future visit if not obtained at baseline.

6.4. On-Treatment assessments

After randomization, participants will be seen in follow up at 4-week intervals for the first 12 weeks and then at 12 week intervals until therapy is completed, as shown in the Time and Event Chart (Appendix 3). For participants having side effects related to treatment or adherence issues, more frequent visits can be undertaken at the discretion of the study physician. These visits will be conducted as an “Unscheduled Visit” and tests/procedures performed will be at the discretion of the study physician (with the exception of adverse events to be managed per guidelines specified in the protocol or manual of operations, i.e. hepatitis flare or hypophosphatemia).

1. Each outpatient visit will include assessment of compliance, adverse events reporting, vital signs, weight, symptoms evaluation, record of concomitant medications, drug dispensing, and blood testing as detailed in the Time and Event Chart (Appendix 3).
2. Symptom questionnaire at each visit.
3. Depression assessments at weeks 12, 24, 36, 48, and 96.
4. Fatigue questionnaire at weeks 24 and 96.
5. Health Behavior and quality of life questionnaires at weeks 48, 96, and 144.

6. Blood will be drawn for CBC with differential at each visit until week 36 and then CBC without differential at week 48, 96, and 144.
7. Hepatic panel (AST, ALT, total bilirubin) at each visit.
8. A renal panel (creatinine, calculated creatinine clearance, phosphate, blood urea nitrogen, and calcium) at every visit from week 12 on.
9. TSH at weeks 12 and 24.
10. Glucose and triglycerides at week 24.
11. There will be a PT/INR, serum uric acid, and other liver tests (albumin, total protein, alkaline phosphatase, direct bilirubin) at weeks 48, 96, and 144.
12. There will be a urinalysis done at weeks 48, 96, and 144.
13. A fasting urine creatinine and phosphate will be done at week 96.
14. For females of childbearing age, adherence to contraception will be reviewed and a pregnancy test repeated at each visit during the peginterferon treatment phase.
15. Qualitative HBeAg (in patients who were HBeAg-positive at baseline visit) and HBsAg at weeks 48 and 96. If there is HBeAg or HBsAg loss then anti-HBe or anti-HBs will be tested.
16. Qualitative HBeAg and anti-HBe (regardless of HBeAg status at the baseline visit) at weeks 144 and 180.
17. Qualitative HBsAg at week 180.
18. Quantitative HBsAg and HBeAg will be tested at every visit from week 12 on.
19. HBV DNA will be drawn at every visit.
20. A blood sample for storing serum and plasma for future research will also be drawn.
21. Antiviral resistance testing at weeks 48, 96, and 144.
22. Ultrasound exam (If clinically indicated, per AASLD guidelines, done as standard of care) at weeks 48, 96, and 144.
23. Fibroscan (if available) no earlier than week 180 visit and no later than week 192 visit

6.4.1 Review criteria for discontinuing treatment and resumption of treatment and post treatment follow up schedule

At the week 180 visit, the scheduled visit prior to the visit at which eligible participants are scheduled to discontinue treatment, a study physician will review the rationale for antiviral withdrawal, criteria for treatment discontinuation, potential benefits and risks, criteria for resuming treatment, and the post treatment follow up schedule with the participants. The study PI will document this discussion in the participant's record. The participant will be provided with a fact sheet that will be reviewed by a study physician and a signed copy maintained in the study record. Participants should be reminded to bring all remaining study medication to the next visit (week 192). Blood will be drawn for qualitative HBeAg, anti-HBe, and HBsAg testing so results are available at week 192. Eligibility to discontinue treatment will be reconfirmed by the study PI on week 192.

6.5 End of Treatment (Week 192)

At week 192, all participants will complete the following:

1. Physical exam.
2. Assessment of adverse events, concomitant medications and adherence
3. Questionnaires (symptoms, quality of life, health behaviors, and fatigue)
4. Depression assessment.
5. Blood will be drawn for CBC, hepatic panel (including albumin, total protein, alkaline phosphatase), renal panel, serum uric acid, PT/INR, anti-HIV, qualitative HBeAg, anti-HBe, anti-HBs, HBsAg, and HBV DNA. A sample of blood will be

stored for eventual assessment of HBeAg and HBsAg concentration, precore/BCP analysis, and antiviral resistance testing.

6. A blood sample for storing serum and plasma for future research will also be drawn
7. Urinalysis and fasting urine creatinine and phosphate.
8. Ultrasound exam (if clinically indicated, per AASLD guidelines, done as standard of care).
9. Fibroscan if available and not performed at, or since, the week 180 visit

At week 192 (year 4), participants who meet study criteria for discontinuing therapy (section 6.5.1) will have treatment stopped.

6.5.1 Eligibility criteria for discontinuing treatment at week 192 (participants must meet all criteria)

Participants will be discontinued from treatment if they meet all of the following criteria as determined based on laboratory results at the week 180 visit and any additional test results and clinical assessment up until the week 192 visit:

1. HBV DNA <1000 IU/mL for the previous 24 weeks (i.e. starting at or before week 156 and continuing through week 180).
2. No cirrhosis (Ishak score 5 or 6) on baseline biopsy
3. Normal indices of liver function (CTP =5), albumin ≥3.8 g/dL, INR ≤1.3, direct bilirubin ≤0.5 mg/dL
4. No clinical evidence of decompensation
5. No clinical or radiologic evidence of portal hypertension
6. Platelet count ≥120,000/mm³
7. HBeAg-negative at baseline visit and confirmed at week 180, or HBeAg-positive at baseline visit with HBeAg loss at or before week 144 and confirmed at week 180. In either situation, there can be no HBeAg positive result at or after week 144.
8. HBsAg-negative (regardless of anti-HBe status), or if HBsAg-positive, HBeAg-negative and anti-HBe-positive at week 180

Participants who do not meet criteria for discontinuing treatment will continue treatment with tenofovir DF until Week 240 or end of the study. Tenofovir DF for the period Week 192 to Week 240 will be provided by the study. Follow up visits and testing will continue every 12 weeks (204, 216, 228) to week 240 or end of the study. If tenofovir DF will be continued beyond Week 240 or end of the study, medication must be obtained per standard of care.

Participants who meet criteria for discontinuing treatment but continue treatment will have follow-up visits and testing per the schedule for participants who discontinue treatment. No study medications (Tenofovir DF) will be provided beyond Week 192 and any antiviral therapy must be obtained per standard of care.

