6.6 Post Treatment assessments (Appendix 4)

1. Outpatient visits will occur at weeks 196, 200, 204, 208, 212, 216, 228, and 240 for participants in both treatment groups.
2. Laboratory testing (liver panel) plus telephone assessment can replace an outpatient visit at weeks 208 and 212 if ALT at the preceding assessment (week 204 and week 208, respectively) is <300 U/L for men or <200 U/L for women and bilirubin is normal (total bilirubin <1.5 mg/dL or direct bilirubin <0.5 mg/dL)

3. Medical history and physical exam at week 240.
4. Clinical evaluation at weeks 196, 200, 204, 208, 212, 216, and 228.
5. Assessment of adverse events and concomitant medications at each visit.
6. Questionnaires (quality of life, depression assessment, fatigue, and health behaviors) at week 240.
7. Symptom questionnaire at each visit.
8. CBC including platelets, alkaline phosphatase, albumin, total protein, and creatinine at week 240.
9. Renal panel (creatinine, calculated creatinine clearance, phosphate, blood urea nitrogen, and calcium) at each study visit for participants who are on Tenofovir
10. Hepatic panel (ALT, AST, albumin, total protein, alkaline phosphatase, total and direct bilirubin) at each visit.
11. Urinalysis at week 240.
12. PT/INR at weeks 196, 200, 204, 216, and 240.
13. Blood samples for serum/plasma at each outpatient visit.
14. Qualitative HBsAg, HBeAg, and anti-HBe at weeks 216 and 240.
15. Anti-HBs and antiviral drug resistance testing at week 240.
16. HBsAg quantification at weeks 204, 216, 228, and 240.
17. HBeAg quantification at weeks 204, 216, 228, and 240.
18. HBV DNA at each outpatient visit
19. Ultrasound exam (If clinically indicated, per AASLD guidelines, done as standard of care) at week 240.
20. Fibroscan (if available and obtained at, or since, the week 180 visit but not later than the week 192 visit) at week 240.

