6.14. Assessment and management of relapse after stopping therapy

6.14.1. Definition of relapse

Virological relapse: Persistent HBV DNA ≥1000 IU/mL during the follow-up period (on at least two samples at least 12 weeks apart, with one of them being more than 24 weeks after stopping therapy) in HBeAg-positive or HBeAg-negative participants.

Biochemical relapse will be defined as an elevated ALT (>30 U/L for females and >45 U/L for males if normal at end of treatment or an increase of 1.5 X end of treatment level if abnormal at end of treatment) on at least two samples at least 12 weeks apart, with one of them being at least 24 weeks after stopping therapy.

An ALT flare will be defined as an ALT level ≥ 300 U/L for males or ≥ 200 U/L for females.

These definitions will be used for data analyses, see section 6.14.2 for criteria to reinitiate treatment.

Monitoring of participants

- Participants with an increase in total bilirubin to ≥ 3 mg/dL or direct bilirubin to ≥ 1 mg/dL or INR ≥ 1.3 (regardless of ALT and HBV DNA levels) must be reassessed as soon as possible and within 1 week for liver panel, PT/INR, CBC, and creatinine. The laboratory testing should continue every week until INR < 1.3 and either total bilirubin < 3 mg/dL or direct bilirubin < 1 mg/dL.
- Participants with an ALT > 1000 U/L for both males and females (regardless of HBV DNA levels) must be reassessed as soon as possible and within 1 week. Thereafter, weekly monitoring of liver panel, bilirubin (total or direct), PT/INR, HBV DNA should continue until ALT ≤ 1000 U/L.
- Participants with an ALT ≥ 300 U/L for males or ≥ 200 U/L for females (regardless of HBV DNA levels) must be reassessed within 1 week and thereafter, every 2 weeks for liver panel, HBV DNA, bilirubin (total or direct), and PT/INR. The laboratory testing should continue until ALT < 300 U/L for males or < 200 U/L for females.
- Participants with an ALT ≥ 150 U/L for males or ≥ 100 U/L for females (regardless of HBV DNA levels) must be reassessed within 4 weeks and thereafter every 4 (± 1) weeks for liver panel, HBV DNA, bilirubin (total or direct), and PT/INR. The laboratory testing should continue until ALT < 150 U/L for males or < 100 U/L for females.

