6.14.2. Criteria for treatment reinitiation in the Post-Treatment Follow up Period

Tenofovir DF will be restarted for any one of the following:

- Any one of the three criteria: INR ≥ 1.3 , total bilirubin ≥ 3.0 mg/dL or direct bilirubin ≥ 1.0 mg/dL, regardless of HBV DNA or ALT level.
- Any clinical decompensation, regardless of HBV DNA or ALT level.
- HBV DNA $\geq 10,000$ IU/mL and ALT > 1000 U/L (male or female) (i.e. only one ALT value > 1000 U/L is needed to qualify).
- HBV DNA $\geq 10,000$ IU/mL and ALT ≥ 300 U/L for males, ≥ 200 U/L for females. A total of one HBV DNA $\geq 10,000$ IU/mL and any three ALT values ≥ 300 U/L (male) or ≥ 200 U/L (female) over the 4-week (or longer) time frame are needed to qualify. Treatment will be resumed if the third ALT remains ≥ 300 U/L (male) or ≥ 200 U/L (female).
- HBV DNA $\geq 10,000$ IU/mL and ALT ≥ 150 U/L for males or ≥ 100 U/L for females. A total of one HBV DNA $\geq 10,000$ IU/mL and any three ALT values ≥ 150 U/L (male) or ≥ 100 U/L (female) over the 12 week (or longer) time period are needed to qualify. Treatment will be resumed if the third ALT remains ≥ 150 U/L (male) or ≥ 100 U/L (female).
- HBsAg-positive and HBeAg-positive at week 192.
- HBsAg-positive, HBeAg-negative, and anti-HBe-negative at week 192

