6.14.3. Management after reinitiation of treatment

Participants who meet criteria for treatment reinitiation specified in section 6.14.2 will be restarted on Tenofovir DF 300mg daily. Tenofovir DF will be provided by the study until week 240. Monitoring of AST, ALT and HBV DNA levels will be done at 4, 8 and 12 weeks after Tenofovir DF is restarted and then every 12 weeks. If bilirubin or INR is abnormal at the time of treatment reinitiation, it (they) should be monitored at 4, 8, and 12 weeks after Tenofovir DF is restarted and then every 12 weeks until it (they) return(s) to normal. If, after treatment reinitiation, the participant meets criteria for non-response (section 6.9) or partial response (section 6.10), the drug therapy will be changed as outlined in those sections.

7. Adverse events and toxicity management

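### A stable INR of exactly 1.3 satisfies both the week 192 stopping rule (≤1.3) and the tenofovir restart rule (≥1.3)

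*Combined protocol and SAP*

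**What the plan says.** **Stopping.** Section 6.5.1 opens "Participants will be discontinued from treatment if they meet all of the following criteria". The third criterion, on liver function, includes "INR ≤1.3, direct bilirubin ≤0.5 mg/dL". Section 6.5 states the consequence: at week 192, "participants who meet study criteria for discontinuing therapy (section 6.5.1) will have treatment stopped". Eligibility rests on the week 180 results plus anything further up to the week 192 visit.

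**Restarting.** Section 6.14.2 lists triggers, any one of which is enough. The first begins "Any one of the three criteria: INR" and sets the INR limit at 1.3 or above, with alternative limits for total bilirubin (≥3.0 mg/dL) and direct bilirubin (≥1.0 mg/dL). It applies at any HBV DNA or ALT level. Section 6.14.3 says that participants who meet a trigger "will be restarted on Tenofovir DF 300mg daily. Tenofovir DF will be provided by the study until week 240".

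**Monitoring.** Section 6.14.1 uses the same INR limit to call for reassessment within one week, and then: "The laboratory testing should continue every week until INR" is below 1.3. Section 6.6 schedules "PT/INR at weeks 196, 200, 204, 216, and 240".

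**Not stopping.** Under section 6.5.1, participants who fail the criteria "will continue treatment with tenofovir DF until Week 240 or end of the study", with drug supplied by the study from week 192 to week 240. Those who meet the criteria but choose to continue get no study drug after week 192.

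**The concern.** The same INR counts as good enough to stop treatment and bad enough to restart it. Nothing in the restart rule asks whether the value has changed since treatment ended, so a participant with no change in liver function can be taken off tenofovir and then be due to go back on.

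Two things are at stake. The first is the participant. Section 7.3.a acknowledges that agents active against HBV carry a warning about hepatitis exacerbation after they are stopped. A withdrawal that must be reversed at once adds that risk for almost no information. The second is the off-treatment data. The endpoints in sections 2.2.3 to 2.2.6 are read 36 and 48 weeks after treatment ends, and a participant restarted at week 196 reaches neither point off treatment. Sites that notice the conflict must either restart without a clinical reason or deviate from a mandatory rule, and may not all choose alike.

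How restarted participants should be counted in the off-treatment endpoints is a separate and wider question, not argued here.

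**Working it through.** The plan gives no figure to reproduce. The check compares the limits directly.

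**1. Overlap of the two INR rules.** Stop if INR ≤1.3 (section 6.5.1); restart if INR ≥1.3 (section 6.14.2).

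| INR | Meets stopping limit | Meets restart limit |
|---|---|---|
| 1.2 | yes | no |
| 1.29 | yes | no |
| 1.30 | yes | **yes** |
| 1.31 | no | yes |
| 1.4 | no | yes |

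The intersection is the single value 1.3.

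**2. Comparison with the other measures used in both rules.**

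| Measure | Stop (6.5.1) | Restart (6.14.2) | Separation |
|---|---|---|---|
| Direct bilirubin | ≤0.5 mg/dL | ≥1.0 mg/dL | 1.0 − 0.5 = 0.5 mg/dL |
| HBV DNA | <1000 IU/mL | ≥10,000 IU/mL, and only with raised ALT | tenfold |
| INR | ≤1.3 | ≥1.3 | none; the limits touch |

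Bilirubin and HBV DNA have a buffer and INR does not, which suggests an oversight. Two of the three ALT-based triggers also require three ALT values, over at least 4 or 12 weeks. The INR trigger requires no repeat.

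**3. Is the value attainable?** Entry criterion 7 in section 4.1 allows INR up to 1.5, so 1.3 is not excluded at entry. No other stopping criterion rules it out: the phrase about normal liver function in section 6.5.1 is spelled out with 1.3 as acceptable.

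**4. Timing.** The eligibility INR falls between week 180 and week 192, and the first post-treatment INR is at week 196.
- Interval between the two readings: 196 − 192 = 4 weeks to 196 − 180 = 16 weeks.
- Off-treatment time if restarted at week 196: 196 − 192 = 4 weeks, and 4/48 = 8.3% of the planned period.
- If the site first waits for the one-week reassessment in section 6.14.1: 5 weeks, and 5/48 = 10.4%.

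**5. After the change to INR <1.3 for stopping.** No value satisfies both INR <1.3 and INR ≥1.3. The smallest gap between a stopping value and a restart value is 1.3 − 1.2 = 0.1 if INR is reported to one decimal, or 1.30 − 1.29 = 0.01 if to two. The documents do not state the reporting precision.

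**The case against.** The strongest reply is that the rules run in sequence. One governs a decision on treatment at week 192 and the other applies only after withdrawal, so nobody is told to stop and continue at the same moment. That is correct, but an unchanged value still leads from a required stop to a required restart.

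Section 6.14.1 could also be read as placing a repeat test before any restart. It requires reassessment within a week, and its opening reference to an increase might be taken to cover INR as well as bilirubin. This would help with an isolated or fluctuating 1.3. It does not help with a stable one, which the repeat would only confirm, and the reference to an increase does not appear in the restart rule.

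The protocol already tolerates quick reversals: section 6.14.2 also restarts participants on certain week 192 serology results. Section 6.4.1 adds a physician's review of both sets of criteria at week 180 and reconfirmation by the investigator at week 192. These steps may catch the case, but a participant at 1.3 is eligible as written. Keeping that participant on treatment would place them among those who meet the criteria yet continue, who lose the study drug supply.

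What stands is the point about size. Anyone stopped must also have no baseline cirrhosis, a CTP score of 5, albumin of at least 3.8 g/dL, platelets of at least 120,000/mm³ and sustained viral suppression. Few such people are likely to have an INR of exactly 1.3 twice. It also stands that the change leaves only a thin margin.

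**Conclusion.** The concern holds. The stopping and restart limits both include 1.3, and nothing elsewhere in the document resolves the overlap. For an affected participant, withdrawal yields about 4 of 48 off-treatment weeks.

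This is a minor point, worth correcting but not one that threatens the trial. It needs an INR reported as exactly 1.3 at eligibility and again 4 to 16 weeks later. The documents give no count of such participants; that the number is small is an assumption, though a reasonable one. The error pushes towards earlier retreatment, and study tenofovir is supplied to week 240 after a restart. The definition of the primary endpoint and the sample size do not depend on it.

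**What to change.** In section 6.5.1, criterion 3, change the INR limit from ≤1.3 to <1.3. Keep the monitoring trigger in section 6.14.1 and the restart trigger in section 6.14.2 at ≥1.3. A participant at 1.3 is then not eligible to stop and stays on study-supplied tenofovir to week 240 or the end of the study.

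Moving the restart trigger to >1.3 would also remove the overlap, but it would loosen a safety trigger and put section 6.14.2 out of step with section 6.14.1.

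The cost is a one-sign protocol amendment with the usual IRB/REB and DSMB notification, and no new data collection. Participants at exactly 1.3 drop out of the off-treatment comparison. The change does not widen the margin: someone stopped at 1.2 who later reads 1.3 still restarts.
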